5.4.3.2 Over 48 weeks and over 96 weeks

Duration of exposure [days] over 48 weeks and over 96 weeks respectively will be calculated as

$$\text{Date of last nintedanib intake}^{[1]} - \text{Date of first nintedanib intake} + 1 \text{ day}$$

^[1] Or Week 48/Week 96 time point (Day 379/Day 715, i.e. 378/714 days after date of Visit 1), if earlier.

In case of last nintedanib intake happened until Week 48/Week 96 time point, half a day will be subtracted assuming that only one capsule was taken on day of last nintedanib intake. Treatment interruptions will not be subtracted from this duration of exposure.

Other variables relative to exposure, such as for example duration of exposure [months] or duration off-treatment, total dose or dose intensity will be derived as defined in Section 5.4.3.1. However, last category for duration of exposure and duration of exposure on actual dose will be “>12 months” for the analyses over 48 weeks and “>18 months” for the analyses over 96 weeks.

5.4.4 Liver enzyme and bilirubin elevations

Liver enzyme and bilirubin elevations will be reported using the following definitions:

- (ALT and/or AST >=3 fold ULN) and bilirubin >=2 fold ULN ^[1]
- ALT >=5 fold ULN and/or AST >=5 fold ULN
- ALT >=3 fold ULN and/or AST >=3 fold ULN

^[1] within a time window of 30 days i.e. the elevation of bilirubin should appear within 30 days after the elevation of AST and/or ALT

The proportion of subjects presenting signs of hepatic injury will be summarised, based on the following definition for signs of hepatic injury:

- ALT and/or AST ≥ 8 fold ULN
- ALT and/or AST ≥ 3 fold ULN and total bilirubin ≥ 2 fold ULN ^[2]
- ALT and/or AST ≥ 3 fold ULN and unexplained INR > 1.5 ^[2]
- ALT and/or AST ≥ 3 fold ULN and unexplained eosinophilia ($> 5\%$) ^[2]
- ALT and/or AST ≥ 3 fold ULN and appearance of fatigue, nausea, vomiting, right upper abdominal quadrant pain or tenderness, fever and/or rash within $+/- 7$ days of the abnormal ALT and/or AST laboratory test result (please refer to [Table 9.3: 1](#) for the list of relevant MedDRA preferred terms to support the derivation of a potential hepatic injury)

^[2] in the same blood draw sample

In addition, maximum individual elevations based on worst value on treatment will be defined as:

- ≥ 3 fold ULN; ≥ 5 fold ULN; ≥ 8 fold ULN for AST and ALT and AST and/or ALT
- ≥ 1.5 fold ULN; ≥ 2 fold ULN for Bilirubin
- $\geq 1.5 \times$ ULN; ≥ 2 fold ULN for alkaline phosphatase (ALK)
- $\geq 3 \times$ ULN for Gamma-Glutamyl-Transferase (GGT)

Note: ULN refers to the Upper Limit of Normal from the central or local laboratory analysing samples from this extension trial.

5.4.4.1 Time-to-event analyses for liver enzyme elevations

Time to first occurrence in extension trial of the above described liver enzyme elevations [days] will be analysed as

Date of event/censoring - Date of first nintedanib intake + 1 day

Subjects with no such event occurred during the trial will be censored according to the mechanism for censoring as described in [Table 5.4.4.1: 1](#).

These times to onset of first event in extension trial will also be summarised in categories:

- <=1 month (31 days)
- >1 to <=3 months (91 days)
- >3 to <=6 months (182 days)
- >6 to <=12 months (365 days)
- >12 to <=18 months (547 days)
- >18 to <=24 months (730 days)
- >24 to <=36 months (1095 days)
- >36 months
- Censored

Further categories might be defined if needed.

5.4.5 Marked changes in vital signs

A marked increase in vital signs is defined as:

- Systolic Blood Pressure >150 mmHg and increase >=25 mmHg above baseline
- Diastolic Blood Pressure >90 mmHg and increase >=10 mmHg above baseline
- Pulse Rate >100 bpm and increase >=10 bpm above baseline,

at any visit.

6. GENERAL ANALYSIS DEFINITIONS

6.1 TREATMENTS

For treatment specifications, please refer to CTP Section 4.

The different periods of interest, as per CTP flow chart, are the following:

Note: the last day of each of the periods is excluded from the period. It defines the first day of the subsequent period.

- Post-IC period (optional^[a]): From date of informed consent to first nintedanib intake.
- Treatment period: From first nintedanib intake (or re-start of treatment if interruption) to last nintedanib intake (or day before start date of interruption if interruption) plus one day.
- Off-treatment (optional^[a]): From start date of interruption to re-start of treatment.
- Residual effect period^[b]: From last nintedanib intake plus one day to last nintedanib intake plus 28 days plus one day.
- Follow-up period (optional^[a]): From last nintedanib intake plus 28 days plus one day (after residual effect period) to last contact date (as collected on the end of study eCRF page) plus one day. This period is only created if last nintedanib intake took place more than 28 days before last contact date (as collected on the end of study eCRF page).
- Post-study period (optional^[a]): From last nintedanib intake plus 28 days plus one day or from last contact date (as collected on the end of study eCRF page) plus one day, whichever occurs later.

^[a] This period is optional insofar as it does not necessarily exist for all subjects.

^[b] In addition, a residual effect period of 7 days will be used for safety analyses to more closely reflect the period of time after the last nintedanib intake.

For subjects who did not receive any dose of nintedanib in extension trial, Post-IC period is the only period defined.

For subjects who died during the trial, periods with above defined start date after date of death do not exist and last existing period is defined until date of death plus one day only.

For safety analyses ([Section 7.8](#)), data from the treatment period, possible off-treatment periods and residual effect period will be considered as on-treatment.

6.2 **IMPORTANT PROTOCOL DEVIATIONS**

No per protocol set analysis will be performed for this study; however, the following list in [Table 6.2: 1](#) below defines the different categories of potentially important protocol deviations (iPD), and it shows whether subjects will potentially be excluded from evaluations performed in this trial. Potentially iPDs will be handled according to BI standards [\(3\)](#). The proportion of subjects with iPDs will be presented for completeness purposes and to demonstrate the adherence to the CTP.

Table 6.2: 1 Important protocol deviations

Category/Code		Description	Requirements	Excluded from
A		Eligibility Criteria		
	A1	
Potential risk related to fetotoxicity
 
a) Women who are pregnant, nursing, or who plan to become pregnant while in the trial
 
b) Women who are of childbearing potential not willing or able to use highly effective methods of birth control per ICH M3
	
a) (exclusion criterion 6 met)
 
b) (inclusion criterion 3 not met)
 
and subject entered the trial
 
Automatic iPD
 
Additional note: In the CTR Table it should show which criteria are violated; however, deviations of multiple sub-categories will only count once towards the overall category.
	None
	A2	Subjects with other underlying diseases or conditions that may put the subject at risk when participating in the trial	
Exclusion criterion 1 met
 
and subject entered the trial
 
Automatic iPD
	None
B		Informed Consent		
	B1	Informed consent not given	
Inclusion criterion 2 not met
 
Automatic iPD
	All
	B2	Informed consent given too late	
eCRF date of informed consent is after date of Visit 1
 
Automatic iPD
 
Additional note: Signature of the wrong IC version, and later signature of the correct one will also be part of this iPD category. This can however only be determined via a manual process.
	None

Table 6.2: 1 Important protocol deviations (continued)

Category/Code		Description	Requirements	Excluded from
C	Trial Medication and Randomization			
	C1	
Trial medication not interrupted
 
a) when ALT or AST \geq 5 fold ULN
 
b) or dose reduced when ALT or AST \geq 3 fold to $<$ 5 fold ULN
	
Based on eCRF dose interruption and lab values between first drug intake and EOT
 
Manual iPd based on MQR outputs
 
Additional note: In the CTR Table it should show which criteria are violated; however, deviations of multiple sub-categories will only count once towards the overall category.
	None
	C2	
Trial medication not permanently discontinued after signs of liver enzyme elevations were observed that
 
a) are indicative of hepatic injury as defined in Section 5.2.5.1.4 and 4.2.1.2 of the CTP
 
b) correspond to ALT or AST \geq 3 fold ULN despite dose reduction or treatment interruption for 2 weeks or more
	
All subjects where signs of liver enzyme elevations are not dealt with according to the requirements of the CTP.
 
Manual iPd based on MQR outputs
 
Additional note: In the CTR Table it should show which criteria are violated; however, deviations of multiple sub-categories will only count once towards the overall category.
	None
	C3	Compliance $>$ 120%	
In case calculated overall compliance is missing: If the answer to the question “Did the patient take trial medication as instructed?” of the eCRF is “No” at at least one of the visits where the compliance cannot be calculated, then an iPd will be flagged. Otherwise no iPd although calculated overall compliance is missing.
 
Manual iPd with review of MQR listings
	None
	C4	
Incorrect trial medication taken
 
a) 150 mg capsules used instead of 100 mg capsules
 
b) 100 mg capsules used instead of 150 mg capsules
 
c) qd instead of bid
	
To be discussed on a case by case basis to determine if iPd
 
Manual iPd with review of MQR listings
 
Additional note: In the CTR Table it should show which criteria are violated; however, deviations of multiple sub-categories will only count once towards the overall category.
	None

Table 6.2: 1 Important protocol deviations (continued)

Category/Code	Description	Requirements	Excluded from
C5	Trial medication interrupted more than 4 weeks for drug-related liver enzyme or bilirubin related AE with duration of more than 4 weeks	To be discussed on a case by case basis to determine if iPD Manual iPD with review of MQR listings	None
C6	More than 16 weeks between ALT, AST or BILI lab tests without trial medication interruption	To be discussed on a case by case basis to determine if iPD Manual iPD with review of MQR listings	None
D	Concomitant Medication		
D1	Subjects who received any other investigational drug during the entire duration of their study participation	Any occurrence of such concomitant therapy is to be flagged as iPD. Manual iPD with review of MQR outputs Additional note: In the CTR Table it should show which medication was taken; however, deviations regarding multiple medications will only count once towards the overall category.	None

Automatic PDs are those detected via an automated programming process using SAS®.

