4.2 OTHER TREATMENTS, EMERGENCY PROCEDURES, RESTRICTIONS

4.2.1 Other treatments and emergency procedures

Rescue medications to reverse the action of nintedanib are not available.

There are no special emergency procedures to be followed.

Dose reduction (from 150 mg bid to 100 mg bid) or treatment interruption should be considered to manage adverse events. No further dose reduction is possible for patients on the 100 mg bid dose. In case of persistent adverse events observed at this dose, or severe effects at 150 mg bid, permanent treatment discontinuation should be considered.

Dose reduction from 150 mg bid to 100 mg bid was possible at Visit 1 if required to manage adverse events identified at the end of the INBUILD® trial.

Treatment interruption and reduction and re-escalation are repeatedly possible.

Table 4.2.1: 1 Allowed treatment reduction / interruption periods

	AEs considered drug related	AEs or other events not considered drug related
Maximum interruption	4 weeks	12 weeks
Recommended restart	with reduced dose (100 mg bid)	with the same dose (100 mg bid or 150 mg bid)
Re-escalation	Any time to 150 mg bid	----

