7.8 SAFETY ANALYSIS

All safety analyses will be performed over the whole trial on the treated set. Similar summaries will be provided regarding the first 48 weeks or the first 96 weeks only.

The analysis of safety data will be based on the concept of treatment emergent AEs or measurements. That means that, for analyses over the whole trial, all AEs/laboratory or vital sign measurements occurring between first nintedanib intake till last nintedanib intake + 28 days will be assigned to the on-treatment period. For analyses over 48 weeks and 96 weeks respectively the on-treatment period is defined from date of first nintedanib intake until date of last nintedanib intake + 28 days, or until Week 48/Week 96 time point (Day 379/ Day 715, i.e. 378/714 days after date of Visit 1), if earlier.

All analyses will be performed according to randomised treatment group in the parent trial and overall.

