7.8.1.1 Exposure adjusted analysis of adverse events

Exposure adjusted analysis of AEs will be presented for analyses over the whole trial. Time at risk and incidence rates per 100 patient-years will be calculated based on the first onset of an AE in the extension trial.

For a specific AE, the total AE time at risk [years] is defined as

$$\frac{\sum \text{time at risk [days] across all contributing subjects}}{365.25}$$

with for each subjects the time at risk [days] defined as follows:

- *Date of first onset of the AE – date of first nintedanib intake in extension trial +1 day*
for subjects with the specific AE

- *End of time at risk – date of first nintedanib intake in extension trial + 1 day*
for subjects without the specific AE.

The end of time at risk is the minimum of either “date of last nintedanib intake + 28 days”, date of last contact date as collected on the end of study eCRF page, date of death or date of the (interim) database lock.

The AE incidence rate [1/100 patient-years (pt-yrs)] will be calculated as

$$\frac{\text{Number of subjects with specific AE}}{\text{Total specific AE time at risk [years]}} \times 100$$

The 95% confidence intervals for incidence rates are derived using the method described by Rothman and Greenland (2008) (12).

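### An AE starting more than 28 days into a treatment gap is on-treatment only if the patient later restarts, so whether it is counted depends on what happens after it

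*SAP*

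**What the plan says.** SAP 6.1 divides each patient's time into consecutive periods. An off-treatment period runs "From start date of interruption to re-start of treatment"; no other end is given. The residual effect period (REP) runs "From last nintedanib intake plus one day to last nintedanib intake plus 28 days plus one day". The final day of a period belongs to the next one, so the REP covers days 1 to 28 after the last dose. Anything later is follow-up or post-study. For safety analyses, "data from the treatment period, possible off-treatment periods and residual effect period will be considered as on-treatment". A footnote adds that "a residual effect period of 7 days will be used for safety analyses" as well.

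SAP 7.8 gives the working window: AEs and measurements "occurring between first nintedanib intake till last nintedanib intake + 28 days will be assigned to the on-treatment period". Protocol 7.3.4 assigns AEs by onset and closes at the same point. SAP 7.8.1 uses AEs after the REP for listings only.

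For the exposure-adjusted rates in SAP 7.8.1.1, a patient with the AE contributes time up to first onset. For a patient without it, "The end of time at risk is the minimum of either" last intake plus 28 days, last contact, death or database lock. Interruptions are not subtracted.

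Protocol Table 4.2.1:1, "Allowed treatment reduction / interruption periods", caps an interruption at 4 weeks for drug-related AEs and at 12 weeks for AEs or other events not considered drug related.

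**The concern.** Two patients can have the same serious AE on day 40 of an interruption. One recovers and restarts: the gap becomes an off-treatment period and the AE is on-treatment. The other dies, or stops for good, without restarting: the last dose is the one before the gap, the REP ended on day 28, and the AE appears only in a listing. What happens after the event decides whether it is counted.

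The summaries at stake are those in SAP 7.8.1 for serious AEs, AEs leading to death and AEs leading to permanent discontinuation. In a long-term safety trial these carry more information than the any-AE count. The denominators are also affected. A restarter's gap days after day 28 remain time at risk, yet anyone who died in those days cannot be a restarter. This is immortal time, and it pulls the rate of fatal AEs down.

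This is a fault of the analysis rule and not of data collection. Protocol 5.2.5.2.1 collects all AEs until the individual patient's end of trial, and a patient in an open interruption is still in the trial.

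**Working it through.** The plan states no figure for this point, so there is nothing to reproduce. The check applies the period rules and then counts days.

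**Step 1: classify by onset day.** Gap day 1 is the first day after the last dose before the gap. A restart, if there is one, is on day 85, after a full 12-week gap. The 7-day column puts 7 in place of 28 in the same rule.

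| Onset, gap day | Restarts on day 85 | Never restarts, 28-day REP | Never restarts, 7-day REP |
|---|---|---|---|
| 5 | on-treatment | on-treatment | on-treatment |
| 8, 20, 28 | on-treatment | on-treatment | listing only |
| 29, 50, 84 | on-treatment | listing only | listing only |

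The rule for deaths in SAP 6.1 only cuts the last existing period at death. It does not turn an open gap into on-treatment time.

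**Step 2: length of the exposed window** (maximum gap minus REP, in days).

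| Maximum gap | 28-day REP | 7-day REP |
|---|---|---|
| 12 weeks, not considered drug related | 84 − 28 = 56 | 84 − 7 = 77 |
| 4 weeks, drug related | 28 − 28 = 0 | 28 − 7 = 21 |

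The zero holds only if the 4-week limit is kept. Deviation C5 in SAP Table 6.2:1 foresees overruns for liver-related AEs.

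**Step 3: illustrate the effect within gap time.** The following are assumptions, because the documents give no values: 100 gaps each planned for 84 days, a constant fatal-AE hazard h per year, each such AE fatal at once, and every survivor restarting.

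- Counted (days 1–28): C = 100 × (1 − exp(−28h/365.25))
- Dropped (days 29–84): D = 100 × (1 − exp(−84h/365.25)) − C
- Person-years kept from days 29–84, restarters only: P = 100 × exp(−84h/365.25) × 56/365.25
- Rate as planned: C / (C/h + P)

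With h = 0.10: C = 0.76, D = 1.51 and P = 14.98. The planned rate is 0.7637 / (7.637 + 14.98) = 0.0338 per year, or 3.38 per 100 patient-years against a true 10.

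| True rate per 100 patient-years | C | D | D/(C+D) | P | Planned rate | Planned/true |
|---|---|---|---|---|---|---|
| 5 | 0.38 | 0.76 | 0.665 | 15.16 | 1.68 | 0.335 |
| 10 | 0.76 | 1.51 | 0.664 | 14.98 | 3.38 | 0.338 |
| 20 | 1.52 | 2.97 | 0.662 | 14.64 | 6.84 | 0.342 |
| 40 | 3.02 | 5.77 | 0.656 | 13.98 | 14.02 | 0.351 |

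Under these assumptions about two thirds of the fatal AEs in a 12-week gap are dropped, and the rate over gap time is about a third of its true value. This describes gap time only, not the whole-trial rate.

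**The case against.** The strongest reply is that the window is the protocol's own. Protocol 7.3.4 defines one continuous period from first dose to the end of the REP, and Protocol 1.2 ties the 28 days to residual drug effect. Most treatment-ending AEs are probably the ones that caused the gap or began early in it, and these are counted whatever their outcome. Drug-related gaps are closed by the 4-week limit under the main REP. Discontinuations still appear in the completion-status table (SAP 7.1) and in the Kaplan–Meier analysis of premature discontinuation (SAP 7.7). Protocol 7.5 mentions survival data, so deaths may also be summarised in text not available for this review.

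Much of this stands, and it limits the point. But the residual-effect argument supports stopping the count 28 days into every gap; it does not support counting later days only for patients who restart. The other tables do not put the missing AEs back into the AE summaries.

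Three stronger readings are tempting, and the documents do not support them.

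- A reader might infer that fatal or treatment-ending AEs from late gap days are zero whatever the true rate. Assignment is by onset, so an AE that starts on day 40, is followed by a restart and only later proves fatal or ends treatment is counted. An imputed last-intake date (SAP 6.6.3.3.1) could also bring an AE back in.
- A reader might take the whole gap as time at risk for the restarter with the day-40 AE. For that AE, time stops at first onset. A non-restarter's time after day 28 is dropped along with the event, so the rate bias comes from event-free restarters' gap days.
- A reader might say that the 7-day analysis fails its purpose. The footnote gives its aim ("a residual effect period of 7 days will be used for safety analyses to more closely reflect the period of time after the last nintedanib"), and that aim concerns the tail after the final dose and not gaps. The fair criticism is only that the same asymmetry starts earlier, on gap day 8.

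**Conclusion.** The asymmetry is real and follows directly from SAP 6.1, 7.8 and 7.8.1.1. It affects new AEs with onset more than 28 days (7 days in the second analysis) after the last dose before a gap. If such an AE is fatal or ends treatment before any restart, it leaves the on-treatment tables, while an AE of the same onset in a restarter stays. AEs starting by gap day 28 are unaffected in the main analysis.

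The exposed window is firm: up to 56 days in gaps not considered drug related and 0 days in drug-related gaps that keep the limit, or 77 and 21 days under the 7-day REP.

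The number of events is not firm. One could assume that 5–15% of about 480 patients have a gap over 28 days, with 28–56 further days off drug. That gives 480 × 0.05 × 28/365.25 = 1.84 to 480 × 0.15 × 56/365.25 = 11.04 patient-years. At an assumed 25–100 events per 100 patient-years, about 0.5 to 11 events would be lost. None of these inputs except the 480 is in the documents, and the upper end needs every such gap to run to the 12-week limit. The range shows only that the size is unknown.

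The primary endpoint, patients with any AE over the whole trial, is probably little affected: a patient interrupted for an AE that began on treatment already counts. The change is worth making for the serious, fatal and discontinuation summaries.

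**What to change.** Keep the protocol-defined main tables and make two additions.

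1. In SAP 7.8.1, add one table of AEs (any, serious, fatal, leading to discontinuation) with onset more than 28 days after the last dose before any gap, up to restart or the individual end of trial. Include restarters and non-restarters alike, and give the matching person-time. Use 7 days for the second analysis.
2. In SAP 7.8 and 7.8.1.1, add a sensitivity version of the on-treatment tables and exposure-adjusted rates. For every patient, events and time at risk stop 28 days (7 days) after the last dose before a gap and resume at restart.

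Record both in SAP section 4 as additions to the planned analysis. The sensitivity run removes the dependence on later outcome and the immortal time; the extra table shows the late-gap AEs that the on-treatment tables leave out.

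The cost is one extra table and one sensitivity run on AEs already collected. In the sensitivity run a few restarters' AEs move out of the on-treatment counts.

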6.3 SUBJECT SETS ANALYSED

- Screened Set (SCS):
This subject set includes all subjects having signed informed consent.
- Treated Set (TS):
This subject set includes all subjects who were dispensed trial medication (nintedanib) and were documented to have taken at least one dose of open-label trial medication (nintedanib).
- Treated Set – 150 mg bid starting dose (TS150S)
This subject set includes all subjects who were dispensed trial medication (nintedanib) and were documented to have taken nintedanib 150 mg bid as starting dose of open-label trial medication.

All evaluations will be based on the treated set (TS), unless otherwise stated.

Subjects will be analysed according to their randomised treatment group in the parent trial (Placebo or Nintedanib) and overall (Total column).

